5.7.4.6 Sustained Pain Freedom from 2 to 48 Hours

Sustained pain freedom is assessed using the number of mITT subjects that experienced no headache pain (response of 0 on Likert scale) at all time points from 2 through 48 hours postdose. Subjects with missing pain scores at no more than 1 time point, given that they have responses of no pain (response of 0 on Likert scale) at the 2, 24, and 48 hour time points will be considered as successes. Subjects with responses missing at greater than 1 time point; missing data at the 2, 24, or 48 hour time point; or with any pain score greater than 0 will be considered as failures.

The results to be presented for the analysis include those described in items (a) through (e) for the primary analysis of pain freedom (Section 5.7.3.1). In this case, the "risk" is the probability of sustained pain freedom from 2 to 48 hours.

5.7.4.7 Sustained Pain Relief from 2 to 24 Hours

Sustained pain relief is assessed using the number of mITT subjects who experience no or mild headache pain (responses of either 0 or 1 on 4-point Likert scale) at all time points from 2 through 24 hours post-dose. Subjects with missing pain scores at no more than 1 time point, given that they have responses of no or mild pain at the 2 and 24 hour time points will be considered as successes. Subjects with responses missing at more than 1 time point, with missing data at the 2 or 24 hour time points, or with any pain score greater than 1 will be considered as failures.

The results to be presented for the analysis include those described in items (a) through (e) for the primary analysis of pain freedom (Section 5.7.3.1). In this case, the "risk" is the probability of sustained pain relief from 2 to 24 hours.

5.7.4.8 Sustained Pain Relief from 2 to 48 Hours

Sustained pain relief will be assessed using the number of subjects that experience no or mild headache pain (response of 0 or 1 on the 4-point Likert scale) at all time points from 2 through 48 hours post-dose. Subjects with missing pain scores at no more than 1 time point, given that they have responses of no or mild pain at all other time points including the 2, 24, and 48 hour time points will be considered as successes. Subjects with responses missing at more than 1 time point; with missing data at the 2, 24, or 48 hour time point; or with any pain score greater than 1 will be considered as failures.

The results to be presented for the analysis include those described in items (a) through (e) for the primary analysis of pain freedom (Section 5.7.3.1). In this case, the "risk" is the probability of sustained pain relief from 2 to 48 hours.

5.7.4.9 Pain Relapse from 2 to 48 Hours

Pain relapse is assessed using the number of mITT subjects that are pain free at 2 hours postdose as the denominator. The numerator is the number of these subjects that then have a relapse of pain at any severity (response of 1, 2, or 3 on the 4-point Likert scale) within 48 hours after administration of study medication. Subjects with more than 1 time point with missing data or with missing data at the 2, 24, or 48 hour time point are classified as relapsers.

The results to be presented for the analysis include those described in items (a) through (e) for the primary analysis of pain freedom (Section 5.7.3.1). In this case, the "risk" is the probability of sustained pain relapse from 2 to 48 hours.

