9.4.2 Secondary Endpoint(s)

If the primary endpoint tests are both significant, then the secondary endpoints are evaluated using a hierarchical gate-keeping procedure, with each test in the hierarchy conducted at $p=0.05$. These secondary endpoints will be tested in the following order:

1. Photophobia freedom at 2 hours
2. Phonophobia Freedom at 2 hours
3. Pain Relief at 2 hours
4. Nausea Freedom at 2 hours
5. Probability of requiring rescue medication within 24 hours
6. Sustained pain freedom from 2 to 24 hours
7. Sustained Pain Relief from 2 to 24
8. Sustained Pain Freedom 2 to 48 hours
9. Sustained Pain Relief from 2 to 48 hours
10. Pain relapse from 2 to 48 hours
11. Proportion of patients able to work or function normally at 2 hours.

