2.3.2 Secondary Estimands

The estimands corresponding to the secondary objectives are shown in Table 2.

The population summary for all secondary estimands is the difference in the percentage of subjects with a positive result ('risk difference') between the BHV-3000 and the Placebo treatment groups.

Photophobia Freedom at 2 hours post-dose	
mITT subjects with photophobia reported as present at migraine onset	
Percent of subjects reporting no photophobia at 2 hours post-dose	
NC=F; RM=F	
Phonophobia Freedom at 2 hours post-dose	
mITT subjects with phonophobia reported as present at migraine onset	
Percent of subjects reporting no phonophobia at 2 hours post-dose	
NC=F; RM=F	
Pain Relief at 2 hours post-dose	
mITT	
Percent of subjects who report mild or no pain at 2 hours post-dose	
NC=F; RM=F	
Nausea Freedom at 2 hours post-dose	
mITT subjects with nausea reported as present at migraine onset	
Percent of subjects reporting no nausea at 2 hours post-dose	
NC=F; RM=F	
Probability of Rescue Medication	
mITT	
Percent of subjects taking rescue medication	
None	
Functional Disability at 2 hours	
mITT	
Percent of subjects with a response of "normal" at 2 hours post-dose	
NC=F; RM=F	
Sustained Pain Freedom (2 to 24 hours; or 2 to 48 hours)	
mITT	
Percent of subjects pain free during the period of interest	
NC1=F; RM=F	
Sustained Pain Relief (2 to 24 hours; or 2 to 48 hours)	
mITT	
Percent of subjects who report no pain, or mild pain, during the period of interest	
NC1=F; RM=F	
Pain Relapse (2 to 48 hours)	
- · · · · · · · · · · · · · · · · · · ·	
mi i i subjects who report bain freedom at 2 nours post-dose	
mITT subjects who report pain freedom at 2 hours post-dose Percent of subjects who report any pain during the period of interest	

Table 2: Estimands for the Secondary Objectives

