5.2.5 Multiple Comparisons

Type I error is controlled in this study by using a hierarchical gate-keeping procedure. First, the family of two co-primary endpoints is tested. If the co-primary endpoints are found to be significant, then secondary endpoints are tested in a fixed sequence. In particular, each co-primary endpoint will be tested for superiority to placebo at a two-sided alpha level of 0.05 without further adjustment for multiplicity. If the primary endpoint tests are both significant, then the following secondary endpoints will be tested in a fixed sequence, in the order shown, with each test conducted at p=0.05:

- 1. Photophobia Freedom at 2 hours
- 2. Phonophobia Freedom at 2 hours
- 3. Pain Relief at 2 hours
- 4. Nausea Freedom at 2 hours
- 5. Probability of Rescue Medication Use
- 6. Sustained Pain Freedom from 2 to 24 hours
- 7. Sustained Pain Relief from 2 to 24 hours
- 8. Sustained Pain Freedom from 2 to 48 hours
- 9. Sustained Pain Relief from 2 to 48 hours
- 10. Pain Relapse from 2 to 48 hours

11. Functional Disability at 2 hours

If a test in the hierarchy is not significant, then any further tests on endpoints in the sequence will have p-values presented only for descriptive purposes, and no conclusions will be drawn from those results.

For exploratory endpoints, no attempt will be made to adjust for multiplicity. Any exploratory endpoints for which p-values are produced will be evaluated at an unadjusted two-sided alpha level of 0.05 and presented only for descriptive purposes.

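### Does testing pain relapse, a comparison among 2-hour responders only, ahead of functional disability at 2 hours weaken the secondary testing sequence?

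*SAP*

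**What the plan says.** Protocol 9.4.2 and SAP 5.2.5 agree on the order. The protocol lists "10. Pain relapse from 2 to 48 hours" followed by "11. Proportion of patients able to work or function normally at 2 hours"; the SAP lists "10. Pain Relapse from 2 to 48 hours" followed by "11. Functional Disability at 2 hours". Each step is tested at 0.05. Under SAP 5.2.5, once a step fails, "any further tests on endpoints in the sequence will have p-values presented only for descriptive purposes".

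The two endpoints have different analysis sets. For relapse, Table 2 in SAP 2.3.2 gives "mITT subjects who report pain freedom at 2 hours post-dose", and SAP 5.7.4.9 repeats this: "Pain relapse is assessed using the number of mITT subjects that are pain free at 2 hours postdose as the denominator". For the endpoint that Table 2 calls "Functional Disability at 2 hours", the population is the whole mITT set, as in SAP 5.7.4.4.

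Relapse is the only step restricted by a post-dose outcome. Steps 1, 2 and 4 use subjects with the symptom present at migraine onset. Steps 3 and 5 to 9 use all mITT subjects.

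**The concern.** Being pain free at 2 hours is a co-primary outcome. If the drug works, the responders in the two arms are different kinds of patient, and comparing relapse between them is no longer a randomized comparison. Such a contrast can fail because of who was selected rather than because of what the drug does.

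The subset is also small, at about 23% of the mITT set on the Phase 2b rates, and unequal between arms. At stake is the formal claim on functional disability at 2 hours: a full-mITT endpoint would lose confirmatory status because of a weaker comparison placed just before it. Exchanging two lines seems to remove the risk at almost no cost.

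**Working it through.** **1. Error control.** In a fixed sequence each step is tested at 0.05 only if all earlier steps succeeded, so familywise error is 0.05 in any prespecified order. The relapse test is valid for its own null hypothesis. The functional estimate and its interval are the same wherever it stands; only its formal status depends on step 10. What remains is a question of power.

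**2. Inputs.**
- Subjects per arm: 90% of 600 = 540 (protocol 9.2, which rounds to about 550).
- Phase 2b pain freedom at 2 hours: 31.4% vs 15.3% (protocol 1.4.2).
- Phase 2b sustained pain freedom from 2 to 24 hours: 27.9% vs 7.4% (protocol 1.4.2).
- Relapse from 24 to 48 hours, and rates of normal function: not given, so varied as assumptions.

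Power = Φ(d/SE − 1.96), with SE = √[p₁(1−p₁)/n₁ + p₀(1−p₀)/n₀].

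**3. The plan's own figure.** Pain freedom at 550 per arm: SE = √[(0.314×0.686 + 0.153×0.847)/550] = 0.0250; d/SE = 0.161/0.0250 = 6.4; power above 0.999. The stated figure of more than 95% is reproduced.

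**4. Power of step 10.** Responders: 540×0.314 = 170 and 540×0.153 = 83, together 253/1080 = 23% of mITT. Implied loss of pain freedom by 24 hours: (31.4−27.9)/31.4 = 11.1% on rimegepant and (15.3−7.4)/15.3 = 51.6% on placebo. Let a further share s of the remaining responders in each arm relapse by 48 hours, so that relapse = L + (1−L)s:

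| s | Rimegepant | Placebo | Power, step 10 |
|---|---|---|---|
| 0 | 0.111 | 0.516 | >0.999 |
| 0.1 | 0.200 | 0.565 | >0.999 |
| 0.2 | 0.289 | 0.613 | 0.999 |
| 0.3 | 0.378 | 0.661 | 0.993 |
| 0.4 | 0.467 | 0.710 | 0.972 |
| 0.5 | 0.556 | 0.758 | 0.917 |

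Responders counted as relapsed because of missing data under SAP 5.7.4.9 enter the same arithmetic as part of s, if missingness is similar in both arms.

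**5. Power of step 11.** With 540 per arm and assumed placebo rates of normal function of 20, 25, 30, 35 and 40%:

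| Difference | 20% | 25% | 30% | 35% | 40% |
|---|---|---|---|---|---|
| 5 points | 0.504 | 0.453 | 0.419 | 0.397 | 0.384 |
| 8 points | 0.871 | 0.829 | 0.795 | 0.772 | 0.757 |
| 10 points | 0.969 | 0.950 | 0.934 | 0.921 | 0.913 |

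**6. Net effect of a swap.** Let R and F be success of the relapse and functional tests, given that steps 1 to 9 passed. As written, relapse is claimed with probability P(R) and function with P(R and F). After a swap these become P(R and F) and P(F). The expected number of claims therefore changes by P(F) − P(R), whatever the dependence between the tests. A swap helps only where function has the higher power.

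- For s = 0 to 0.4, relapse power exceeds functional power in all 5×15 = 75 combinations. The closest is 0.972 against 0.969.
- For s = 0.5, function has the higher power in 4 of 15 combinations, all at a 10-point difference. The largest gain is 0.969 − 0.917 = 0.05.
- Example, s = 0.3 and function 30% vs 38%, with independence assumed to split the parts: the functional claim gains 0.795×(1−0.993), about 0.005; the relapse claim loses 0.993×(1−0.795), about 0.20.

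**The case for a change.** The strongest reply is that Phase 2b may not repeat, and that selection can distort relapse in a way that no power figure repairs. Suppose patients who would be pain free on either treatment relapse at 40%, those pain free only on the drug relapse at 60%, and the drug alters relapse in nobody. The rimegepant rate is then (0.153×0.40 + 0.161×0.60)/0.314 = 50.3% against 40% on placebo, a 10-point difference against the drug.

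With smaller true differences, step 10 can indeed fail. At 50% placebo relapse its power is 0.32, 0.62 and 0.87 for differences of 10, 15 and 20 points. If function were 25% vs 35% (power 0.950) and the relapse difference 10 points, the functional claim would have probability 0.32×0.95 = 0.30 as written and 0.95 after a swap, with independence assumed.

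This is sound as logic but rests on rates that the documents do not support. The 24-hour figures imply a difference of about 40 points in favour of rimegepant. With placebo relapse at 52%, rimegepant relapse would have to reach about 33% before power fell to 80%.

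It can also be said that the meta-analysis sequence in SAP 5.7.5 puts relapse last. That sequence contains only the five durability endpoints, in the same relative order as steps 6 to 10 of SAP 5.2.5. Functional disability is not in it, so it says nothing about relapse against function.

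What stands is a point of reading: the relapse result describes recurrence among 2-hour responders and is not a randomized comparison. Protocol 3.2 and SAP 2.3.2 and 5.7.4.9 already state that denominator, and steps 6 to 9 already test durability in all mITT subjects before relapse is reached.

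**Conclusion.** The concern does not hold. The two documents agree with each other, type I error is controlled, and no rule or analysis is wrong. The order of the last two steps is a choice about where to spend power. On the protocol's Phase 2b rates, step 10 has power of 0.97 or more for up to 40% further loss after 24 hours and 0.92 at 50%, so it would seldom block step 11. A swap would usually place the better-powered test behind one for which the documents give no rates.

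This rests on three assumptions: the Phase 2b 2-hour and 24-hour rates carry over; the same further share is lost in both arms from 24 to 48 hours; and normal function on placebo is 20 to 40%, with differences of 5 to 10 points. If the relapse difference were only 10 to 15 points, the other order could do better. That makes the order a matter on which statisticians may differ, not a fault in the plan.

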5.7.5 Durability Endpoints Evaluated by Meta-Analysis

The durability endpoints (e.g., pain freedom from 2 to 24 hours) will be analyzed in a metaanalysis that uses the data from both BHV3000-301 and BHV3000-302. These endpoints will be tested in a fix sequence, in the order shown below, with each test conducted at a two-sided alpha level of 0.05.

- 1. Sustained Pain Freedom from 2 to 24 hours
- 2. Sustained Pain Relief from 2 to 24 hours
- 3. Sustained Pain Freedom from 2 to 48 hours
- 4. Sustained Pain Relief from 2 to 48 hours
- 5. Pain Relapse from 2 to 48 hours

For the durability endpoints, the meta-analysis will mirror the primary analysis, with the addition of strata to represent each study. The common risk difference is computed using CMH weights, stratified by the use of prophylactic migraine medication (yes or no) and study (BHV3000-301 or BHV3000-302). For each endpoint, the risk difference is tested at a two-sided alpha level of 0.05. If a stratum (prophylactic medication use: yes or no) has sparse data (less than 5 subjects) then the strata will be pooled.

Results presented for each analysis include the following:

- The number and percentage of subjects who are successes or not successes on the endpoint of interest. These are presented by strata and treatment group, with ASE, and 95% asymptotic CIs.
- Common risk difference with sample size, p-value, ASE, and 95% asymptotic CIs.
- Risk difference within each strata with sample size, p-value, ASE, and 95% asymptotic CIs.
- A plot of the risk differences within each strata and common risk difference.
- Common risk for each treatment with sample size, ASE, and 95% asymptotic CIs.
- The common risk difference, with ASE, is also computed separately for each of the two studies.

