5.3 Planned Analyses

The analyses planned for endpoints that use data from this study only will be conducted after the last subject completes their End of Treatment Visit or discontinues from the study, and the database has been locked.

A meta-analysis of the durability endpoints will be conducted after the last subject in BHV3000-301 and BHV3000-302 completes their End of Treatment Visit or discontinues from the study, and both databases have been locked.

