5.7.4 Secondary Efficacy Endpoints Evaluated with Data from the Current Study

If the co-primary endpoint tests are both significant, then the secondary endpoints are evaluated using a fixed sequence approach, with each test in the hierarchy conducted at p=0.05. See Section 5.2.5 for the testing order.

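### The five durability endpoints are tested at 0.05 in the conditional in-study sequence and again at 0.05 in a pooled 301+302 sequence that the available text neither makes conditional, nor charges to a shared alpha, nor labels supportive

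*SAP*

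**What the plan says.** SAP 5.2.5 sets out eleven secondary tests in fixed order, each at 0.05, entered only if both co-primaries are significant. The durability endpoints hold ranks 6 to 10, from "6. Sustained Pain Freedom from 2 to 24 hours" through pain relapse to 48 hours. After a failed test, later p-values are descriptive and "no conclusions will be drawn from those results". Protocol 9.4.2 gives the same order and does not mention pooling.

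SAP 5.7.5 takes the same five endpoints, in the same order, on combined data from studies 301 and 302. They are to be "tested in a fix sequence, in the order shown below, with each test conducted at a two-sided alpha level of 0.05". The only condition elsewhere is timing, in 5.3: "A meta-analysis of the durability endpoints will be conducted after the last subject in BHV3000-301 and BHV3000-302 completes their End of Treatment Visit" or discontinues, with both databases locked.

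On the status of the two sets:

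- 5.7.4 is headed "Secondary Efficacy Endpoints Evaluated with Data from the Current Study", adds "See Section 5.2.5 for the testing order", and defines all five in-study analyses (5.7.4.5 to 5.7.4.9).
- Table 2 lists them as secondary estimands. Appendix 1 titles their tables as secondary analyses and lists no 301+302 table.
- 5.7.5 stands between the secondary section and the exploratory section, 5.7.6. The descriptive-only statement in 5.7.6 covers exploratory endpoints.
- Section 7 uses the word supportive for the analyses in Appendix 3. The meta-analysis is not among them, and section 7 does not list it as an addition to the protocol.

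**The concern.** The same five clinical questions can be answered by two formal tests, each at the full 5% level, and the text available does not say which answer counts. Two situations need to be kept apart.

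In the first, the in-study sequence passes rank 5. Both the in-study and the pooled test of sustained pain freedom from 2 to 24 hours are then live. If either may support a claim, that endpoint has two correlated chances.

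In the second, the in-study sequence stops before a durability endpoint. SAP 5.2.5 then rules out any conclusion on it, but 5.7.5 can still declare it significant. This is not a doubled chance. It is a way round the condition that 5.2.5 imposes.

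In both situations, which result supports a durability claim stays open until the data are known.

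**Working it through.** **1. The plan's own level.** In a fixed sequence a test counts only if every earlier test was rejected, so an error requires rejecting the first true null reached, with probability at most 0.05. The in-study sequence therefore holds 0.05 as stated. So does the pooled sequence taken alone. Together the simple bound is 0.05 + 0.05 = 0.10. The tests share the 301 data, so the actual figure is lower.

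**2. Second situation: no arithmetic needed.** Suppose rank 4 fails in study 301. Under 5.2.5, ranks 5 to 11 become descriptive. Under 5.7.5, the first pooled test runs at two-sided 0.05 without reference to that failure. A null durability endpoint then has a 5% chance of being declared significant where 5.2.5 allows none.

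**3. First situation.** Let s be study 301's share of the pooled information. Then Z_pooled = √s · Z_301 + √(1−s) · Z_302, and the correlation of Z_301 with Z_pooled is √s. With the endpoint null in both studies:

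- two-sided error = 1 − P(|Z_301| < 1.96 and |Z_pooled| < 1.96)
- error in the drug's favour = 1 − P(Z_301 < 1.96 and Z_pooled < 1.96)

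The documents do not give study 302's size, so s is assumed.

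| s | √s | Two-sided (nominal 5%) | Drug's favour (nominal 2.5%) |
|---|---|---|---|
| 1/3 | 0.577 | 8.8% | 4.4% |
| 1/2 | 0.707 | 8.3% | 4.2% |
| 2/3 | 0.816 | 7.7% | 3.8% |

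With 0.025 for each test instead, the two-sided figure is 4.3% at s = 1/2 (4.5% at 1/3, 4.0% at 2/3).

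**4. What keeping only the in-study route costs.** Reaching rank 6 requires nausea freedom at rank 4. Protocol 1.4.2 gives Phase 2b rates of 67.4% and 51.2%, a difference of 0.162. Protocol 9.2 gives 90% of 600 = 540 treated per arm (stated there as about 550). Power ≈ Φ(d/SE − 1.96), with SE = √{[p1(1−p1) + p2(1−p2)]/n} and the placebo rate held at 0.512:

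- full effect: SE = √[(0.2197 + 0.2499)/540] = 0.0295; 0.162/0.0295 = 5.49; power above 99.9%
- half effect (0.593): SE = √[(0.2414 + 0.2499)/540] = 0.0302; 0.081/0.0302 = 2.69; power 77%
- one third (0.566): SE = √[(0.2456 + 0.2499)/540] = 0.0303; 0.054/0.0303 = 1.78; power 43%

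These figures use all 540 per arm, but Table 2 restricts the test to "mITT subjects with nausea reported as present at migraine onset". If 60% qualify (assumption), n = 324 and the three powers are 98.9%, 55% and 28%. The chance of reaching rank 6 cannot exceed the power of this one test. Freedom from the most bothersome symptom and rescue use have no Phase 2b rates in the documents and can only lower it.

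**The case against.** The strongest reply is that the structure of the SAP already answers the question. Section 5.2.5 speaks of error control in this study, 5.3 separates analyses using this study's data from the later cross-study analysis, and 5.7.4, Table 2 and Appendix 1 all treat the in-study tests as the secondary analyses. On that reading only a label is missing. The description of the structure stands: it does point to the in-study tests as this study's formal secondary tests. But it does not make 5.7.5 supportive. A supportive estimate needs neither a fixed testing order nor an alpha level, and 5.7.5 states its level both for the sequence and for each endpoint.

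A second reply is that the rule may be written elsewhere. SAP section 3 is redacted and study 302's SAP is not available. This stands as a limit: the gap is shown only for the text at hand.

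A third is that 8.3% presumes that either result may support a claim and that the endpoint is null in both studies although ranks 1 to 5 passed. That also stands. A reader might infer that the trial's error rate is 8.3%; the documents do not support that. The figure belongs to one permissive reading, for one endpoint. The early-stop problem depends neither on that premise nor on study 302's size.

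A reader might also infer that the pooled tests were added after the data were seen, because section 7 and Appendix 3 are in the past tense. Those passages do not cover the meta-analysis, and 5.3 and 5.7.5 are in the future tense. The documents do not settle the timing.

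**Conclusion.** The point holds as a gap in stated error control for the durability endpoints. Followed as written, 5.7.5 can declare significance at 5% where 5.2.5 allows no conclusion. If the in-study sequence reaches rank 6 and either result counts, the first durability endpoint, null in both studies, has about 8.3% two-sided error instead of 5%, or 4.2% instead of 2.5% in the drug's favour. The two-sided range of 8.8% to 7.7% rests on an assumed 301 share of one third to two thirds. The in-study hierarchy taken alone holds 0.05, and neither the co-primaries nor ranks 1 to 5 are affected.

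It would go too far to credit all of the pooled test's power to skipping the in-study conditions. At one third of the Phase 2b effect on sustained pain freedom from 2 to 24 hours (27.9% against 7.4%), the in-study test has about 95% power once rank 6 is reached. The pooled test has 99.4% or more if study 302 has the same effect, over the same range of shares. Part of the gain is simply sample size.

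**What to change.** State in 5.2.5 and 5.7.5 that in-study ranks 6 to 10 are the confirmatory route and that the 301+302 meta-analysis is supportive: estimate, confidence interval and nominal p-value, with no claim. List it in section 7 as an addition to the protocol. If unblinding has already occurred, report the pooled p-values as nominal in the study report. This changes wording only and keeps every estimate.

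If the sponsor wants a confirmatory pooled claim, type I error must be shared explicitly and agreed with study 302's SAP. Options include:

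- splitting alpha, 0.025 for each durability sequence. This bounds the durability endpoints at 0.05. To hold 0.05 across all secondaries, the pooled sequence must also wait for rank 5; otherwise the bound is 0.05 + 0.025 = 0.075;
- starting the pooled sequence only after the in-study sequence has been passed;
- moving ranks 6 to 10 out of the in-study sequence, with a stated entry condition for the pooled tests and a matching change to protocol 9.4.2.

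The cost of the default fix is the unconditional second route to a durability claim. So far as the Phase 2b rates go, that loss is negligible at the full effects. It is larger if effects shrink: rank 4 alone caps the chance of reaching rank 6 at about 77% at half effect and 43% at one third, and lower if only some subjects have nausea at onset.
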